## **5.0 Study Population / Inclusion and Exclusion Criteria**

We aim to recruit 45 participants (15 in each group: A, B, and C). Inclusion criteria include: 1) age 18+; 2) daily nicotine-containing e-cigarette user (25+ days per previous month); 3) e-cigarette use 5+ times/day; 4) e-cigarette use > 1 year; 5) smoking >1 cigarette on 5-7 days per week 6) interest in quitting smoking and e-cigarette within the next month (>7 on 10-point scale); 7) willingness to use NRT; 8) able to receive text messages/email, and 8) mailing address in SC.

Exclusion criteria includes medical conditions contraindicated to NRT use (including pregnancy, past month myocardial infarction, current cardiac arrhythmia, current angina, uncontrolled vascular disease, or medical conditions in which consumption of phenylalanine is contraindicated, including Phenylketonuria [PKU] and allergy to phenylalanine), individuals reporting current use of other nicotine-containing products and/or smoking cessation medications, those who vape non-nicotine substances, and individuals unable to consent (e.g. significant cognitive deficit, non-English speaking). These criteria were used in the proof-of-concept study which recruited at an acceptable pace. Exclusion criteria, including health information, will be ascertained via self-report on the online pre-screener. We have requested a waiver of signed consent for this assessment.

Pregnancy status will be ascertained via self-report on the online pre-screener. In addition, we will ask participants if they are sexually active and if they are using any type of contraceptive method (with a list of available options). If female participants are deemed eligible (i.e., not pregnant and not engaging in unprotected sex) and schedule an intake, they will be mailed a pregnancy test. They will be told they will not complete the test until after they have consented to the study and agree to continue. During consent, discuss the exclusion criteria for pregnancy, as well as review risks of medication use as it pertains to pregnancy. Following consent, during the initial intake assessment, we will conduct the pregnancy test. The participant will perform the pregnancy test at home and report results to the research staff via sending a photo of the test (if doing consent over phone) or showing the test on video (if consenting via video call). If the test is negative, we will continue with the rest of the study procedures.

We will not be enrolling vulnerable populations, specifically pregnant women, children, prisoners, or institutionalized individuals. We also will not enroll subjects incapable of providing their own consent. Should a potential subject present where there is a concern about their ability to understand study procedures and provide meaningful consent, their cognitive status and understanding of the study will be evaluated by the investigative team. If there is any concern that the individual may be impaired, they will not be eligible for participation and not enrolled in the study. The rationale will be provided to

the individual as well as his or her family members. Referrals for further evaluation, including urgent or emergent evaluation, will be made as needed and clinically warranted.

## **6.0 Number of Subjects**

We aim to recruit 45 participants (15 in each group: Arm A (21mg patch, qd + 4mg lozenge prn [minimum of 5 & up to 20 per day]); Arm B (21mg patch + 14mg patch qd + 4mg lozenge prn [minimum of 5 & up to 30 per day]), or Arm C (2X21mg patches qd + 4mg lozenges prn [minimum of 5 & up to 40 per day]). We will use all possible methods to recruit until each arm is full.

## **7.0 Setting**

We will use exclusively remote/telehealth procedures as detailed below. Data will be stored on MUSC Box or OneDrive folders which will only be shared with study staff. Any paper copies of data will be stored in a locked office in the HCC building.

## **8.0 Recruitment Methods**

Advertising will be done online through a variety of media outlets seeking dual users motivated to quit. Participants will be screened online for eligibility. Potential participants will complete a pre-screening survey that is linked in the ad. If the individual is deemed eligible, the research staff will conduct a screening appointment via the web/mobile phone with the participant to confirm eligibility. After confirming eligibility, the research staff will conduct a full consent and intake via the tele-consent platform (i.e., Doxy.me or other HIPAA compliant tele-video conferencing software) or a link to a REDCap consent form.

This research study will use remote/telehealth procedures as detailed below, consistent with our Tobacco Treatment Program procedures at our institutions.

## **9.0 Consent Process**

When interested participants enter into the online screening survey via REDCap, they will be provided with information about the purpose of the screening survey, including what information will be collected, and how it will be kept private. Participants will be aware that they will be providing contact information and health information on this survey, which will only be used for research study eligibility purposes and will be kept secure. Participants have the option to stop the screening survey at any time. Upon review of the provided information, participants will provide consent to screening by selecting the appropriate option on REDCap, which will be recorded as consent (signature waived). Eligible participants will be contacted following the screening to consent into the study as outlined below.

Participants will have 2 options to consent into this study: 1) remote consent via a virtual procedure (i.e., Doxy.me or other HIPAA compliant tele-video conferencing software), or 2) remote electronic consent (e-consent) via REDCap combined with a phone call. Informed consent will be maintained in each, allowing (requiring) discussion with study staff to ensure full understanding. In each option, participants will schedule a remote consent “visit” with research staff and will be encouraged to be in a private location during the call. Participants will be provided with a copy of the consent form electronically, which they can review on their own. Research staff will review the consent form with participants during the visit, allowing for any participant questions to be answered. The participant will be encouraged to take as much time as needed to review the consent form prior to enrolling in the study. Participants will also be notified that they will receive a signed copy of the consent form for their personal records to reference in the future.

Remote consent via doxy.me: This essentially is video or telephone facilitated live discussion with study staff and potential study participant. After the initial determination of study eligibility, assessed online in

our secure survey, participants will be asked about their capacity for doxy.me procedures, including access to a computer with a webcam and speakers, and compatible internet browser (doxy.me is currently optimized for Google Chrome & Firefox, with planned expansion to additional browsers). For those who have the required hardware and software for doxy.me, we will offer this option and follow IRB-approved procedures as per precedent. All doxy.me signed consent forms will be saved as pdf files within our study records; the participant also gets an electronic copy. Research staff will then have the participant complete the baseline questionnaire.

**Remote e-consent via REDCap:** This is similar to above doxy.me procedures but without the video connection, replaced by live phone call. Participants will link to a REDCap-delivered consent document and will have a concurrent phone discussion with study staff who will provide further details on the study and answer any questions. Like doxy.me procedures above, these will likely be scheduled with potential participants in advance, i.e., through a consent appointment. The individual would electronically sign the consent form, and this then becomes a part of the research record, and like above the participant is given an electronic version of the consent to retain.

For all the above procedures, and throughout the study, we maintain a phone line to support anyone who calls with questions. Anyone who completes a consent form will comprise the consented sample. However, the sample is reduced further to those with whom we can establish phone contact (Day 0; weekly follow-up surveys will begin the following day); i.e., the enrolled sample. This enrolled sample is the intent-to-treat sample.

Although the mode of consent may differ across participants (i.e., doxy.me vs. teleconsent) we have taken steps to ensure that all participants will be fully informed of study procedures, including risks/benefits of participation, prior to providing signed consent. We ensure that all potential participants discuss the study with an IRB-approved consenter prior to providing signed consent.

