## **10.0 Study Design / Methods**

A target of 45 dual users across South Carolina will be recruited through various media outlets. Advertising will solicit vapers motivated to quit. Dual users will consent to be screened online for study eligibility, including potential for pregnancy. Pregnancy status and health conditions contraindicated to NRT (past month myocardial infarction, current cardiac arrhythmia, current angina, uncontrolled vascular disease, or medical conditions in which consumption of phenylalanine is contraindicated, including Phenylketonuria [PKU] and allergy to phenylalanine) will be ascertained via self-report on the online pre-screener. In addition, we will ask participants if they are sexually active and if they are using any type of contraceptive method (with a list of available options). If female participants are deemed eligible (i.e., not pregnant and not engaging in unprotected sex) and schedule an intake, they will be mailed a pregnancy test. They will be told they will not complete the test until after they have consented to the study and agree to continue. During consent, we will discuss the exclusion criteria for pregnancy, as well as review risks of medication use as it pertains to pregnancy and the aforementioned medical conditions.

If the participant qualifies, research staff will schedule a time to complete the interview and baseline assessment battery. Following consent, during the initial intake assessment, we will conduct the pregnancy test on applicable participants. If the test is negative, we will continue with the rest of the study procedures. Participants will then be randomized to study arm (Arm A (21mg patch, qd + 4mg lozenge prn [minimum of 5 & up to 20 per day]); Arm B (21mg patch + 14mg patch qd + 4mg lozenge prn [minimum of 5 & up to 30 per day]), or Arm C (2X21mg patches qd + 4mg lozenges prn [minimum of 5 & up to 40 per day]). Participants will be provided with a 28-day supply of NRT by mail and a self-help booklet (which includes instructions for medication use) and instructions to select a target quit date within 1 week. Research staff will contact the participants upon receipt of the materials and obtain the

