target quit date. Participants in both groups will receive a brochure with information for contacting the SC QuitLine. During the 28-days of treatment, participants will be sent daily monitoring surveys asking about e-cigarette use, cigarette smoking, NRT, and quit attempts during the previous day. One month following the receipt of the materials, participants will complete an assessment battery. All assessment procedures will be completed via approved remote data collection platforms (e.g. REDCap). Participants will have the option to receive all study-related surveys (through REDCap) via text message or via email. No identifying information will be included on the texts/emails.

**Randomization.** Participants will be randomized to one of the following NRT conditions: Arm A (21mg patch, *qd* + 4mg lozenge *prn* [minimum of 5 & up to 20 per day]); Arm B (21mg patch + 14mg patch *qd* + 4mg lozenge *prn* [minimum of 5 & up to 30 per day]), or Arm C (2X21mg patches *qd* + 4mg lozenges *prn* [minimum of 5 & up to 40 per day]). Randomization to the intervention groups will be stratified on dependence score as follows: Participants will complete both the Roswell ENDS Nicotine Dependence Scale (Roswell eND; e-cigarette dependence) and the Fagerström Test for Nicotine Dependence (FTND; smoking dependence). Both scales have score ranges from 0 (no dependence) – 10 (high dependence). Consistent with cutoffs for the Roswell eND scale, participants will be stratified by low dependence (0-5) or high dependence (6-10) based on their highest score on either scale.

**Treatments.** All treatment procedures will be conducted remotely (e.g., online, through mail).

**Intervention:** Following randomization, participants will be instructed to select a quit day (Day 0) within the next week at which time they will commence using NRT. Participants will be sent a supportive text message reminder on that date (“*Today is your quit date! Make sure to use your medications and written materials to help you. You got this!*”).

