**NRT medications.** Following consent, participants randomized to the combined intervention will be mailed their 28-day supply of NRT. All participants will be encouraged to use the highest dose sent to them based on their randomization. A specific emphasis will be made on instructing participants to use both patches and lozenges concurrently. We will allow participants to engage in dose reductions naturally if they feel they need to, which will be captured through the daily surveys. Although this medication has not been formally tested for ENDS cessation, with the exceptions of our small pilot studies, it is the first line treatment for cigarette cessation. For this reason, we believe it is a safe and acceptable pharmacotherapy to use for this intervention. We will monitor adverse events.

**Behavioral Support.** A brief, informational booklet will be provided to participants that discusses how to plan and engage in a quit attempt of all tobacco products used. This will be adapted from currently used treatment manuals utilized by the MUSC Tobacco Treatment Program with clinical patients. This booklet will also provide information regarding the SC QuitLine, a freely available public service that provides tobacco cessation counseling and medication over the phone or through mobile/web platforms. Participants will be informed about the services the QuitLine offers as well as how to contact this service.

**Daily Monitoring.** During the 28-days of treatment, all participants will be sent daily monitoring surveys (described later). All assessment procedures will be completed via approved remote data collection platforms (e.g., texting via Redcap). To increase retention, we will call participants who do not respond for  $\geq 3$  days.

**Follow-up.** At the end of treatment (Day 28), research staff will contact the participant to complete an assessment battery. Four weeks after this (Day 56), a final follow-up assessment battery will be administered. Those who report abstinence from smoking will be mailed a remote carbon monoxide monitor (iCO) to complete and return. To increase retention, surveys will be sent via text and email, and we will call participants who do not respond within 1 week.

**Measures.** Dual users who enroll in the study will first complete an assessment battery.

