## Assessments

[figure not shown]
- Demographics (Baseline): Demographics will include sex, gender, sexual orientation, race, ethnicity, age, income, education, marital status, and health insurance status.
- E-cigarette Use History (Baseline): At baseline participants will report e-cigarette use history (length of e-cigarette use, device, flavor, why they started, past quit attempts), current weekly use rates (days per week, estimated times per day, estimated puffs per day, length that a cartridge/refill lasts) and details about their specific product typically used (type, flavors, nicotine content, size of cartridge/refill).
- Cigarette Use History (Baseline): Participants will report retrospective (lifetime) and current weekly (past 7-day) use of cigarettes, including length of time smoking, brand smoked, cigarettes per day, and quit attempts.
- Motivation and Confidence to quit (Baseline, Days 28, 56): Participants will be asked to rate on a scale of 1-10, 10 being highest, their level of motivation and confidence in their upcoming quit attempt. If still using ENDS/smoking at end of treatment or follow-up, this will be re-assessed.
- Expectancies (Baseline). Expectancies for e-cigarette use will be measured using the Short Form Vaping Consequences Questionnaire (S-VCQ) and expectancies for smoking will be measured using the Smoking Consequences Questionnaire (SCQ).
- Dependence (Baseline, Days 28, 56). Participants will complete the Roswell eND Scale, which has been validated to measure dependence on individuals seeking to quit ENDS use, as well as the Fagerström Test of Nicotine Dependence (FTND).
- Daily monitoring survey (Treatment [Days 1-28]): In addition to the primary endpoints above, daily surveys will ask about the previous day: attempts to quit e-cigarettes/smoking, cravings to vape (Vaping Craving Questionnaire), cravings to smoke (Questionnaire of Smoking Urges), and NRT use (number of patches and/or lozenges used). Participants will also be asked if they used the supportive booklet or engaged with the Quitline, and length of each interaction.
- Withdrawal (Treatment [Days 1-28]): Symptoms of withdrawal will be measured using the Brief Wisconsin Inventory of Smoking Dependence Motives (WISDM) scale.

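### The only written intent-to-treat definition turns on phone contact on Day 0, not on randomisation; read literally, it can exclude randomised people who are not reached

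*Combined protocol and SAP*

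**What the plan says.** Section 9.0 starts from everyone who completes a consent form and then narrows the group: "the sample is reduced further to those with whom we can establish phone contact (Day 0; weekly follow-up surveys will begin the following day". It concludes: "This enrolled sample is the intent-to-treat sample". Neither sentence refers to randomisation. The same section already requires a live conversation at consent: "Informed consent will be maintained in each, allowing (requiring) discussion with study staff to ensure full understanding".

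Section 10.0 gives the sequence of procedures. After consent and intake, including a negative pregnancy test where one applies, "Participants will then be randomized to study arm". The materials are then posted, and staff contact participants when they arrive to obtain the target quit date. In the Intervention paragraph, which begins after randomisation, "participants will be instructed to select a quit day (Day 0) within the next week", and NRT starts on that day. The Assessments list has an entry beginning "Daily monitoring survey (Treatment [Days 1-28".

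Section 11.0 commits to the ITT principle and concludes from it that missing data should cause no difficulty. It names no analysis set. It counts abstinence from the start of treatment. Section 4.0 scores non-response and missing data as not abstinent, but does not say whose data are covered. It uses enrolled people as the denominator for Day 28 completion.

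**The concern.** An ITT set is fixed by randomisation. Here the one explicit definition is fixed by whether someone answers the phone on a day whose only other use in the protocol is a day after randomisation. If that is the day meant, membership depends on a post-randomisation event. People assigned to an arm who are not reached would never enter the set, so the section 4.0 scoring rule would never apply to them.

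The section 11.0 reassurance about missing data needs everyone randomised to be in the set. If they are not, the comparison is no longer between the groups that were randomised, and with 15 per arm a few people matter. The same definition sets the denominator for Day 28 retention, a feasibility endpoint. If the text stays as it is, the choice of set could be made after it is known who was reached.

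**Working it through.** The plan gives no figure that depends on this definition, so there is nothing to reproduce beyond 3 × 15 = 45. The check has two parts: what the text says about order, and how large the effect could be.

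**1. Does the text place the phone contact before or after randomisation?** No sentence orders the two, and the indirect pointers conflict.

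| Pointer | Suggests |
|---|---|
| Day 0 in section 10.0 is the quit day, chosen after randomisation | After |
| Surveys start the day after the contact (section 9.0); daily surveys cover treatment Days 1 to 28 (Assessments) | After |
| Section 10.0 has a staff contact when the materials arrive (mode not stated, not called Day 0) | After, weakly |
| Consent already involves live discussion, so a further contact step looks like a later one (section 9.0) | After, weakly: the interview and baseline battery scheduled in section 10.0 could be that step |
| The feasibility endpoint has contact preceding enrolment (section 4.0) | At or before |
| Medication is posted once a person has enrolled (section 16.0) | At or before |
| 45 allocated (section 11.0) and 45 enrolled (section 12.0) | At or before |

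Neither reading leaves the text clean. If contact comes later, randomised people can be lost from the set. If it comes earlier, Day 0 has two meanings, and section 9.0 starts surveys the day after a call made before any quit day was chosen.

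**2. How large could the effect be if contact comes later?** The documents give no contact-failure rate, so 1, 2 or 3 unreached people out of 15 is an assumption. Unreached people contribute zero abstinent days under section 4.0. Let p be the arm's abstinence probability with all 15 kept and k the number dropped.

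Estimate after dropping = p × 15/(15 − k). The factors are 15/14 = 1.07, 15/13 = 1.15 and 15/12 = 1.25. Days = 28 × the estimate. The values of p come from the section 11.0 power ranges.

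| p | All 15 kept | k = 1 | k = 2 | k = 3 |
|---|---|---|---|---|
| 0.10 | 2.80 days | 3.00 | 3.23 | 3.50 |
| 0.15 | 4.20 days | 4.50 | 4.85 | 5.25 |
| 0.30 | 8.40 days | 9.00 | 9.69 | 10.50 |

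**3. Which way does the between-arm difference move?** Assume 0.10 (standard) and 0.30 (augmented) with all 15 kept in each arm.

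- All randomised: 28 × (0.30 − 0.10) = 5.6 days.
- Three dropped from the augmented arm only: 28 × (0.375 − 0.10) = 7.7 days.
- Three dropped from the standard arm only: 28 × (0.30 − 0.125) = 4.9 days.
- Three dropped from each: 28 × (0.375 − 0.125) = 7.0 days.
- Equal rates and equal losses: no difference either way.
- Reached people equal at 0.30, three unreached in one arm only: the contact-based set shows 0 days; the all-randomised set shows 28 × (0.30 − 0.30 × 12/15) = 1.68 days.

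The direction is therefore not fixed.

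**4. Scale against precision.** The approximate 90% confidence half-width for 0.10 versus 0.30 is 28 × 1.645 × √[(0.09 + 0.21) × DE/(28 × 15)], with DE = 1 + 27 × ICC. At ICC 0.2, DE = 6.4 and the half-width is about 3.1 days. At ICC 0.5, DE = 14.5 and it is about 4.7 days. The largest shift from the 5.6-day base case in step 3 is 7.7 − 5.6 = 2.1 days.

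**5. Retention.** The pilot's end-of-treatment completion was 24/30 = 80%. Applied to 45, that is 36 completers. If the unreached are among the 9 non-completers, dropping 1, 2 or 3 in total gives 36/44 = 81.8%, 36/43 = 83.7% or 36/42 = 85.7%, against 36/45 = 80.0%.

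**The case against.** The harmful reading fits parts of the procedures poorly. On the quit day, section 10.0 schedules a text reminder, not a call. The contact on arrival of materials is not called Day 0 or said to be by phone. Section 16.0 has enrolment before posting, which a contact on or after arrival would contradict. People reach randomisation through a live intake. Section 11.0 commits to ITT, which ordinarily means all randomised, and the section 4.0 scoring rule is not limited to people reached by phone. The losses used above have no source, and the resulting shifts are smaller than the confidence half-width.

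Much of this stands. It makes the harmless reading credible and rules out any claim about actual size. It does not settle the matter. Section 11.0 states a principle and section 4.0 a scoring rule; neither says who is in the set, and the one sentence that does uses a different criterion. Low precision does not excuse an avoidable bias.

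A reader might infer more: that the sponsor intends to exclude randomised participants, or that the results will favour the augmented arms. The documents support neither, since the order is unsettled and the direction depends on which arm loses people. Nor should weight be put on section 9.0 calling the surveys weekly, or on section 10.0 timing an assessment from receipt of the materials. Both look clerical and do not affect who is analysed.

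**Conclusion.** The concern holds as a defect of definition. The plan's only written ITT definition does not mention randomisation and ties membership to phone contact on Day 0, a label used elsewhere for a day after randomisation. Read literally, it can remove randomised people from the analysis, in conflict with the plan's own ITT commitment. That this will happen is not established: on the alternative reading, with contact at or before randomisation, the bias is zero and only the double use of Day 0 remains.

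The size cannot be known from the documents. The inflation factors of 1.07 to 1.25 for one arm rest on an assumed 1 to 3 losses out of 15 and on scoring those people as not abstinent throughout. The wording should be corrected before any analysis.

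**What to change.** - Replace the section 9.0 definition with all randomised participants, analysed in the arm assigned, and repeat it in section 11.0. State that people not reached stay in the set and are scored as not abstinent under section 4.0.
- Use the number randomised as the denominator for Day 28 retention.
- Give Day 0 one meaning in sections 9.0, 10.0 and 11.0. Sections 10.0 and 11.0 already agree on the quit day, when treatment starts. Use another name for the section 9.0 phone contact and say whether it comes before or after randomisation.

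The cost is wording only; no procedure changes. Abstinence and retention may look slightly less favourable than on a contact-based set.
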